4. SUBJECT RECRUITMENT AND COMPENSATION

4.1 Recruitment

Subjects will be recruited by posting flyers in designated areas around USU's campus, through advertisements on social media. In the advertisement, potential subjects for this study will be directed to contact the study team by email or phone to obtain more information about the study, if interested. Participants who are interested will be provided with a copy of the informed consent by email. When the participant expresses interest in being in the study, the study team member will confirm by telephone that the participant meets most of the inclusion/exclusion criteria (ones that can be determined without

Version 1 Page 6 of 9

the need for a blood draw) before scheduling him/her for a consent meeting. Subjects will attend a one-on-one information session that will be conducted by trained member to present the details of the study. We anticipate that we will need to telephone screen, approximately 150 people and that approximately 45 will be consented. We will enroll up to 30 participants to meet our goal of having at least 24 participants complete the study (assuming a 20 % drop-out rate).

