7. ANALYTICAL PROCEDURES AND STATISTICAL CONSIDERATIONS

- o **Inflammation:** Inflammatory biomarkers (IL-6, VCAM-1, TNF-alpha and C-reactive protein [CRP]) will be measured using ELISA kits at Dr. [name]'s laboratory at Utah State University. Plasma samples will be stored at -80°C until cytokine analyses are performed.
- Metabolomics: Mass spectrometry techniques will be used for untargeted and/or targeted assessment of blood and/or urinary metabolites. This analysis will give insight into the appearance of food-derived metabolites in the human body and how they may impact inflammatory responses after eating. This analysis will be performed using de-identified samples by Metabolon Inc (a company dedicated to metabolomics analysis) and/or the Plant for Human Health Institute. Samples will be provided to these core services as de-identified samples. No other data will be shared with these core services. Plasma and urine samples will be stored at -80°C until metabolomics analyses are performed.

Version 1 Page 7 of 9

- o **Dietary logs:** The Diet History Questionnaire III (NIH) and 3-day food records will be analyzed by dietetic staff within Dr. [name]'s laboratory at Utah State University.
- Statistical analysis: Change scores (post-dietary intervention baseline) will be created for all inflammatory biomarkers and metabolites. Metabolic intermediate data will be reduced into Metabolic Factors using Principal Component Analysis (PCA) of the change scores. Factor scores will be computed for each individual for both diets. Change scores and factor (change) scores for both diets will be compared using paired t-tests. P< 0.05 will be considered statistically significant and analyses will be performed in SAS 9.4 (SAS, Cary, NC).

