- o **Power Calculations:** Using untargeted metabolomics for our power calculations of the number of participants we need to recruit, we assume a P-value ≤ 0.05, Q-value ≤ 0.3, and standard deviation of 0.3 based on previous work (Pimentel et al., 2018). Since there are no entirely comparable previous studies available to draw from, the effect size and number of truly different metabolites are meant to give general estimates. 600 metabolites are typically identified (Nieman et al., 2015) and conservative estimation is that 20-40 metabolites will be significantly different with a mean of 0.2624 (30% difference). An n=24 per group is expected to provide true discovery rates ranging from 89-93 % assuming differences in 80-120 metabolites. Assuming a drop-out of 20%, the final number of participants we will recruit is N=30. This, we consider adequate without having to engage more participants than necessary to address the research aims.

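### The sample-size figure of 89-93% is given for 80-120 differing metabolites, not for the 20-40 the plan calls conservative, and the rate is not defined

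*Combined protocol and SAP*

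**What the plan says.** Section 7 (Power Calculations) bases the sample size on untargeted metabolomics. It sets the inputs: "we assume a P-value ≤ 0.05, Q-value ≤ 0.3, and standard deviation of 0.3 based on previous work". About 600 metabolites are expected, and the plan's "conservative estimation is that 20-40 metabolites will be significantly different with a mean of 0.2624 (30% difference"). It adds that "the effect size and number of truly different metabolites are meant to give general estimates".

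The result is then stated for a different count: "An n=24 per group is expected to provide true discovery rates ranging from 89-93 % assuming differences in 80-120 metabolites". With 20% drop-out this becomes N=30, of which the plan says: "This, we consider adequate without having to engage more participants than necessary to address the research aims". Section 4.1 repeats "our goal of having at least 24 participants complete the study" and gives no further basis for it.

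The Statistical analysis paragraph of section 7 says "Change scores and factor (change) scores for both diets will be compared using paired t-tests". Its only threshold is on P ("0.05 will be considered statistically significant and analyses will be performed in SAS 9.4"); the Q-value limit does not appear there.

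**The concern.** Within two consecutive sentences the assumed number of differing metabolites moves from 20-40 to 80-120, with no explanation. The result is quoted only for the larger count, which is two to six times the conservative one (80/40 = 2, 120/20 = 6). The count matters because, at a fixed false discovery rate, fewer true differences force a stricter P cut-off and so lower sensitivity.

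The rate itself is not defined. It could mean sensitivity (the share of real differences that are found) or the share of flagged metabolites that are real. The plan also leaves open the sidedness, the false-discovery method, which threshold governs, and whether 0.3 is the SD per diet or of the within-person difference. The per-group wording suggests an unpaired calculation, although the design is a crossover analysed with paired t-tests.

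No other calculation supports 24 completers and 30 enrolled, so a reader cannot tell what the study can detect under the plan's own cautious assumption.

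**Working it through.** **Inputs from section 7.** Difference d = 0.2624 (= ln 1.30), SD 0.3, n = 24, M = 600 metabolites, P<=0.05, Q<=0.3, and m1 truly different metabolites.

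**Assumptions, not in the documents.** Metabolites are independent with a common effect. Tests are two-sided unless stated. Any within-person correlation r is assumed.

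**Drop-out.** 24/(1 - 0.20) = 30, which agrees with the plan.

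**Reading 1: share of flagged metabolites that are real.** Even at 100% power, the share at P<=0.05 is at most m1/(m1 + 0.05 x (600 - m1)).
- m1 = 80: 80/(80 + 26) = 75.5%
- m1 = 120: 120/(120 + 24) = 83.3%

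Q<=0.3 targets only about 1 - 0.3 = 70%. Neither rule gives 89-93%.

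**Reading 2: sensitivity.** Power comes from the noncentral t distribution:
- unpaired: d/(0.3 x sqrt(2/24)) = 3.030, 46 df
- paired, 0.3 per diet: the SD of the difference is 0.3 x sqrt(2(1 - r)). At r = 0 the noncentrality is 3.030, 23 df; at r = 0.2 it is 3.388, 23 df
- paired, 0.3 as SD of the difference: 0.2624/(0.3/sqrt(24)) = 4.285, 23 df

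At P<=0.05 alone, sensitivity is 84.3% (unpaired), 82.7% (paired, r = 0) and 98.4% (SD of difference 0.3). These values do not depend on m1, so this rule cannot explain a range quoted across 80-120.

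At Q<=0.3 without the P cut-off, the P cut-off a solves m0 x a/(m0 x a + m1 x power(a)) = 0.3 with m0 = 600 - m1 (exact FDR). Benjamini-Hochberg (BH) replaces m0 by 600 in the numerator. Sensitivity (%):

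| Setting | 20 | 40 | 80 | 120 |
|---|---|---|---|---|
| Unpaired, exact | 62.3 | 74.8 | 85.6 | 90.8 |
| Paired, r = 0, exact | 56.5 | 71.3 | 83.9 | 89.9 |
| Paired, r = 0.15, exact | 68.3 | 80.4 | 89.8 | 93.9 |
| Paired, r = 0.2, BH | 71.5 | 82.0 | 89.8 | 93.0 |
| Paired, r = 0, one-sided, BH | 69.7 | 81.4 | 90.0 | 93.5 |
| Unpaired, one-sided, exact | 74.3 | 84.7 | 92.6 | 95.9 |
| Paired, SD of difference 0.3, exact | 93.8 | 97.0 | 98.9 | 99.5 |

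The stated 89-93% is matched by paired r = 0.2 with BH, and approached by the r = 0.15 and one-sided settings. These give about 68-85% at 20-40. The literal unpaired two-sided reading gives 86-91% at 80-120 and 62-75% at 20-40.

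**Both thresholds together.** At 20-40 the Q rule is the stricter in every two-sided exact setting checked (the largest cut-off is 0.0297, below 0.05), so adding P<=0.05 changes nothing there. At 80-120, sensitivity cannot exceed its value at P<=0.05. With exact FDR, P<=0.05 is the stricter rule at both 80 and 120. With BH, Q is the stricter at 80 in the unpaired and r = 0 settings (cut-offs 0.0449 and 0.0438), giving 83.1% at 80 against 84.3% at 120 (unpaired) and 81.0% against 82.7% (r = 0).

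**P<0.05 alone, as in the Statistical analysis paragraph.** At 20-40 true differences, the share of flagged metabolites that are real is 37-55% (unpaired) or 40-58% (SD of difference 0.3).

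**The case against.** The strongest defence is that 89-93% may be a correct sensitivity for 80-120. Ordinary choices reach it, and the plan's failure to list them does not make the figure wrong. This stands. A reader might infer an arithmetic error, but the documents do not support that. What is shown is that the figure does not apply to the count called conservative: the same choices give lower values at 20-40.

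A second defence is that the plan labels the effect size and the count as general estimates, because no fully comparable study exists. This lowers the weight placed on either number, but it does not explain naming one count as conservative and reporting only another.

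A third is that 20-40 might be the number declared significant and 80-120 the number truly different. That does not fit: at 84.3-98.4% sensitivity, 80-120 true differences would yield about 67 (80 x 0.843) to 118 (120 x 0.984) true discoveries.

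Per group may simply mean per diet, since the crossover and paired tests are clear elsewhere. The source cited for the SD may also say which kind of SD it is. Both are fair, so these are gaps in reporting, not proof that the wrong calculation was done.

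It is also tempting to say that P<=0.05 is always the stricter rule at 80 and 120, so that no range could arise under the joint rule. That holds for exact FDR but not for ordinary BH, and the plan does not name its method.

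**Conclusion.** The point holds as an internal inconsistency in the sample-size justification. The stated 89-93% is for 80-120 differing metabolites, the plan's conservative count is 20-40, no result is given for that count, and the rate is undefined. The textual mismatch needs no modelling.

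Its size depends on choices the plan does not state. Settings that come close to the stated figure give about 68-85% sensitivity at 20-40, and the literal unpaired two-sided reading gives 62-75%. With 0.3 as the SD of the paired difference, 20-40 gives 94-97%. A reader might therefore infer that 24 completers are too few, but the documents do not show this.

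All these percentages rest on independent metabolites and a common effect. The correlations are assumptions, since the documents give none. The point should be fixed, but it does not threaten the design.

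**What to change.** Amend the text of section 7; no added enrolment is proposed.

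- Use one count throughout: 20-40, or 80-120 with a reason.
- Define the rate as sensitivity or as the share of flagged metabolites that are real.
- State the sidedness, the false-discovery method, and which threshold governs (P<=0.05, Q<=0.3 or both). Make the Statistical analysis paragraph agree.
- State whether 0.3 is the SD per diet, with the within-person correlation assumed and its source, or the SD of the paired difference.
- Replace the per-group wording and 89-93% with the result recomputed for 24 crossover completers and paired t-tests at the chosen count. At 20-40 and Q<=0.3 (two-sided), this is 94-97% if 0.3 is the SD of the difference (exact FDR). If 0.3 is per diet, it is about 57-71% at correlation 0 (exact FDR), rising with positive correlation (71.5-82.0% at 0.2 with Benjamini-Hochberg).

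The cost is a short text correction. The downside is that the restated figure may be less favourable than 89-93%.

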8. DATA STORAGE AND CONFIDENTIALITY

Clinical study data (including screening data, food logs, questionnaires, satiety responses, bloodwork) will be collected and managed using REDCap (Research Electronic Data Capture). REDCap is a secure web application designed to support data capture for research studies, providing user-friendly web-based case report forms, real-time data entry validation (e.g. for data types and range checks), audit trails and a participant coded data export mechanism to common statistical packages (SPSS, SAS, Stata, R/S-Plus). The system was developed by a multi-institutional consortium initiated at Vanderbilt University. REDCap servers are hosted in the College of Education & Human Services at Utah State University, where data will be stored and processed. REDCap data collection projects rely on a thorough study-specific data dictionary defined in an iterative self-documenting process by all members of the research team. This iterative development and testing process results in a well-planned data collection strategy for individual studies. REDCap is flexible enough to be used for a variety of types of research and provides an intuitive user interface for database design and data entry. Coded clinical data will be stored indefinitely on REDCap and/or USU's Box. The enrollment log, with participant names/addresses that can be linked back to participant codes, which is kept on the [name] Lab Shared Drive on USU's box will be destroyed 3 years after completing the study. It is anticipated that all manuscripts will be published at that time and have been sent to interested study participants. Online activity always carry with them a risk of breach. Participants will be made aware of these potential threats and risks to their confidentiality.

Biospecimens will be stored in a -80°C freezer at the Center for Human Nutrition Studies for the duration of sample collection. All samples will be stored using coded labels. Blood samples collected during screening will be sent to Labcorp for routine bloodwork. Once all biospecimens have been collected from all participants, all biospecimens will be transported to a -80°C freezer in the Nutrition and Food

Version 1 Page 8 of 9

Science building for long-term storage (maximum of 20 years). Any participant coded analytical data (including inflammatory biomarkers, metabolomics data, and analyzed food log data) will be kept on the [name] Lab Drive at USU's Box Drive to be accessed only by [name] [name] and his study staff. Study records that identify subjects will be kept confidential as required by law. Federal Privacy Regulations provide safeguards for privacy, security, and authorized access. Except when required by law, they will not be identified by name, social security number, address, telephone number, or any other direct personal identifier in study records disclosed outside of Utah State University. For records disclosed outside of USU, they will be assigned a code number. The key to the code will be kept on the [name] Lab Drive at USU's Box Drive. For participants that choose to withdraw from the study after biospecimens have been collected, they will have three years to instruct the research team on whether they'd like the unused identifiable blood and urine samples destroyed or if they would like the samples to be used for other research. After the three year time period, information samples will be de-identified and it will not be possible to know whose is whose.

9. DATA SAFETY AND MONITORING

All study members will have completed CITI- and other institutional training pertinent to the study. Any unanticipated problems will be reported to the USU IRB by the PI as per institutional policy.

